9.6.2.2 Continuous Endpoints

The indirect comparisons will use LS mean differences and their standard errors.

In order to provide LS means similar in methodology to those seen in the UNVEIL study, the LS mean differences will be taken from simple ANOVA models at Week 16 with only treatment group and country included in the model. Participants with missing data at Week 16 will have their last observed value before Week 16 carried forward.

For comparison with ADVANCE study, the LS mean differences will be taken from a Bayesian mixed model for repeated measures as described for the main analytical approach for the primary analysis. No additional imputation will be done for this analysis.

$\text{LSMD}_{\text{EDP1815}}$ = LS mean difference from placebo for EDP1815

$\text{LSMD}_{\text{Apremilast}}$ = LS mean difference from placebo for Apremilast

$\text{SE}_{\text{EDP1815}}$ = SE of $\text{LSMD}_{\text{EDP1815}}$

$\text{SE}_{\text{Apremilast}}$ = SE of $\text{LSMD}_{\text{Apremilast}}$

$$\text{LSMD for Indirect Comparison (LSMD}_{\text{Indirect}}\text{)} = \text{LSMD}_{\text{EDP1815}} - \text{LSMD}_{\text{Apremilast}}$$

$$\text{SE for Indirect Comparison (SE}_{\text{Indirect}}\text{)} = \text{SE}_{\text{Indirect}} = \sqrt{\left[\text{SE}_{\text{EDP1815}}^2 + \text{SE}_{\text{Apremilast}}^2\right]}$$

$$95\% \text{ CI for LSMD for Indirect Comparison} = \text{LSMD}_{\text{Indirect}} \pm 1.96 \times \text{SE}_{\text{Indirect}}$$

9.6.2.3 Apremilast UNVEIL study (NCT02425826)

The UNVEIL study was performed on a population of moderate participants. The population of interest was defined as those with baseline PGA=3 and baseline BSA 5-10%. For the indirect comparisons with data from this study, the subgroup of participants which match those criteria will be used.

The following endpoints will be compared at Week 16:

- Achievement of PASI-50 (binary)

- Achievement of PASI-75 (binary)
- Achievement of PGA score of 0 or 1 (binary) – note that all participants achieving this must also have ≥ 2 point reduction from baseline as all participants in this analysis have PGA=3.
- Percentage change from baseline in PGA*BSA (continuous)

9.6.2.4 Apremilast ADVANCE study (NCT03721172)

The ADVANCE study was performed in a population of mild/moderate participants. The criteria specified for PGA, BSA or PASI for recruitment into this study were broadly similar to those for this study, therefore the results from the full mITT population will be used for comparison.

The following endpoints will be compared at Week 16:

- Achievement of PGA score of 0 or 1 with ≥ 2 point reduction from baseline (binary)
- Change from baseline in PASI score (continuous)

It should be noted that at the time of writing this SAP, the results were not yet available on clinicaltrials.gov for this study. This analysis will only be performed if these results are published prior to DB lock for this study.

10 Safety Analyses

The Safety population will be used for all summaries of Safety. All safety endpoints will be listed.

10.1 Extent of Exposure

The duration of exposure (days) and number of doses taken will be summarized using summary statistics for continuous data. The number and percentage of participants with at least 4, 8, 12 and 16 weeks (28, 56, 84 and 112 days respectively) will also be presented.

Treatment start and stop dates, exposure duration (days), number of doses administered, number of capsules taken and reasons for dose adjustments and dose interruptions will be listed by participant.

10.2 Adverse Events

Adverse events will be reported from the date of signed informed consent and through for 28 days after cessation of dosing. Adverse events occurring after the 28 days post-treatment would only be reported if the investigator considers it to be related to the study treatment.

Only treatment emergent AEs (TEAEs) will be included in the summaries, pre-treatment AEs will be included in the listings of all AEs.

In the primary analysis at the end of Part A, only adverse events which started on or before date of the end of Part A will be included in the summaries.

In the final analysis at the end of Part B, only adverse events which started during Part B will be included in the summaries. Treatment related events which start in Part B and any Part A AEs which change in Part B will be included in the relevant data listings.

All AEs will be coded using version 23.0 of MedDRA. Severity of event will be coded using the Common Terminology Criteria for Adverse Events v5.0 (CTCAE).

An overview of TEAEs will be produced showing the number and percentage of participants with:

- Any TEAEs (Part A)
- Any TEAE of CTCAE grade 2 or above (Part A)
- Any TEAE of CTCAE grade 3 or above (Part A)
- Any TEAE of CTCAE grade 4 or above (Part A)
- Any fatal TEAE (Part A)
- Any serious TEAE (Part A)
- Any TEAE leading to permanent discontinuation of study drug (Part A)
- Any TEAE leading to withdrawal from the study (Part A)
- Any related TEAE (Part A and Part B)
- Any related TEAE of CTCAE grade 2 or above (Part A and Part B)
- Any related TEAE of CTCAE grade 3 or above (Part A and Part B)
- Any related TEAE of CTCAE grade 4 or above (Part A and Part B)
- Any related fatal TEAE (Part A and Part B)
- Any related serious TEAE (Part A and Part B)
- Any related TEAE leading to permanent discontinuation of study drug (Part A and Part B)
- Any related TEAE leading to withdrawal from the study (Part A and Part B)

Related events are those which were considered by the investigator to be possibly, probably or definitely related to study drug.

TEAEs will also be summarized by system organ class (SOC) and preferred term (PT). Summary tables will contain the number and percentage of participants and the number of events. A participant who has multiple events in the same SOC or the same preferred term will be counted only once in the participant counts but all events will be counted in the event counts. Adverse event summaries will be sorted by the internationally agreed SOC order ([Table 9](#)) and decreasing incidence of preferred term within SOC in the EDP1815 column.

In the primary analysis the above summary will be repeated for treatment phase TEAEs and follow-up phase TEAEs.

Related TEAEs and TEAEs of CTCAE Grade 3 or above will also be summarized by SOC and PT in the same manner as described above.

Non-serious TEAEs reported by at least 5% of participants in any treatment group will also be summarised by SOC and PT.

In the final analysis only related TEAEs will be summarized by SOC and PT in the same manner as described above.

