5.1 General Study Design and Plan

This is a multicentre, randomised double-blind, placebo-controlled, parallel cohort dose ranging study of participants with mild to moderate plaque psoriasis.

After eligibility is confirmed during the screening period ([Protocol Section 4.1](#)), participants will be randomly assigned in a 1:1:1 ratio to 1 of the following 3 parallel cohorts:

- Cohort 1: 0.8×10^{11} cells of EDP1815 or matching placebo administered as 1 PIC, once daily.
- Cohort 2: 3.2×10^{11} cells of EDP1815 or matching placebo administered as 4 PICs, once daily.
- Cohort 3: 8.0×10^{11} cells of EDP1815 or matching placebo administered as 10 PICs, once daily.

[figure not shown]
In each cohort, approximately 75 participants will be randomly assigned in a 2:1 ratio to receive either EDP1815 or matching placebo once daily for 16 weeks.

As shown in Figure 1, Part A of the study comprises a screening period of up to 4 weeks, a baseline visit, a treatment period of 16 weeks, and a follow-up visit at Week 20, making 11 scheduled study visits in total. On completion of Part A, the primary analysis will be performed.

Part B of the study is designed to assess the durability of treatment response and incidence of rebound of psoriasis following cessation of dosing. All participants will attend for skin assessments at Weeks 24 and 28, unless they have previously experienced treatment failure and/or had rebound of disease. A final visit at Week 40 will also be performed for those participants who experienced treatment response at Week 16 but have not yet met the definition of complete relapse. Part B therefore comprises a maximum of 3 additional scheduled study visits with a follow-up of up to 40 weeks (24 weeks after cessation of dosing). On completion of Part B, the final analysis will be performed.

‘Treatment failure’ is synonymous with ‘starting a new psoriasis treatment’ which is an oral agent, biological, or intermediate or high-potency dose topical therapy for plaque psoriasis. Starting topical unmedicated emollients and low-potency topical steroids which were not taken at baseline does not count as starting a new psoriasis treatment.

Figure 1 Study Schema

Note: PIC=Powder in capsule (formulation). All dosing is once daily.

Note: Since this figure was produced for the protocol, the Interim Analysis has been moved from Week 12 to when the last participant has received their last dose (Week 16).

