5.3.4.2 Treatment-Emergent Adverse Events

An adverse event (AE) will be classified as ‘treatment-emergent’ if the onset date/time was on or after the start date/time of study treatment. Where dates or times are missing or partially missing, AEs will be assumed to be treatment-emergent, unless there is clear evidence (through comparison of partial dates/times, see [Section 7.3.1](#)) to suggest that the AE started prior to dosing.

AEs will be classified into the following study phases based on the onset date/time of the AE after any imputations:

- Pre-Treatment Phase: All AEs with onset date/time prior to the first dose of randomized study treatment
- Treatment Phase: All AEs with onset date/time at the time of or after the first dose of randomized study treatment (Day 1) up to and including the date of the last dose of treatment received.
- Follow-up Phase: All AEs with onset date after the date of the last dose of treatment received.

For participants who complete 16 weeks of dosing per protocol the Treatment Phase will be from Day 1 to Day 112 and the Follow-up Phase will be from Day 113 until their last day in the study. In all cases the day will be assumed to start at 00:00 hours and end at 23:59 hours. Adverse events occurring in both the Treatment Phase and Follow-up Phase are classified as treatment emergent.

For the primary analysis which considers only data collected in Part A, only events which start on or prior to the end of Part A date will be included in the adverse event summaries.

The onset phase of all AEs will be included in the relevant data listings.

For the final analysis, only treatment related events which start in Part B will be included in the adverse event summaries.

Only treatment related events which start in Part B and any Part A AEs which change in Part B will be included in the relevant data listings.

6 Sample Size

The sample size of 225 participants in total, has been chosen to explore the tolerability and safety of EDP1815. Although the study will use a model-based probability inference approach in a Bayesian framework, the following power calculation was also performed (using a basic frequentist approach) in order to give confidence that enough participants are available to find a clinically meaningful difference between active dose and placebo if the below assumptions are met.

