7.1.6 Part B Population

The Part B population will consist of all participants who entered Part B of the study.

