7.3.2 Adverse Event Information

AEs with missing relationship will be considered 'Related' for summary purposes but recorded as missing in the listings.

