15.5.3 Data Listings

Number	Title	Population	Programming notes
16.2.8.1.1	Reasons for Withdrawal from Part B	Part B	
16.2.8.1.2	Visits Missed Due to COVID-19 in Part B	Part B	
16.2.8.1.3	Concomitant Medications Started or Changed in Part B	Part B	
16.2.8.2.1	Individual Components of the PASI Questionnaire – Part B Visits	Part B	
16.2.8.2.2	PASI Endpoints– Part B Visits	Part B	
16.2.8.2.4	PGA Score– Part B Visits	Part B	
16.2.8.2.5	BSA and PGA*BSA – Part B Visits	Part B	
16.2.8.2.6	LSS Items and Score– Part B Visits	Part B	
16.2.8.2.7	DLQI Items and Score – Part B Visits	Part B	

Number	Title	Population	Programming notes
16.2.8.2.8	mNAPSI Items and Score – Part B Visits	Part B	
16.2.8.2.9	PSI Items and Total Score – Part B Visits	Part B	
16.2.8.3	Adverse Events Started or Changed in Part B	Part B	

16 Appendix 2: Psoriasis Area and Severity Index Score

Intensity

A representative area of psoriasis is selected for each body region (head and neck, upper limbs, trunk, lower limbs).

The intensity of erythema (redness), induration (thickness) and desquamation (scaling) of the psoriasis in each body region is scored as:

- 0 = None
- 1 = Mild
- 2 = Moderate
- 3 = Severe
- 4 = Very Severe

An intensity score is calculated for each body region as the sum of the three scores for erythema, induration and desquamation.

- A1 = Intensity score for head and neck
- A2 = Intensity score for upper limbs
- A3 = Intensity score for trunk
- A4 = Intensity score for lower limbs

Each subtotal is multiplied by the body surface area represented by that region as follows:

- B1 = 0.1 x A1
- B2 = 0.2 x A2
- B3 = 0.3 x A3
- B4 = 0.4 x A4

Percentage area affected

The percentage area affected by psoriasis is evaluated in each of the four body regions. In each body region the area is expressed as:

- 0 = not affected at all
- 1 = >0% - <10%
- 2 = 10% - <30%
- 3 = 30% - <50%
- 4 = 50% - <70%
- 5 = 70% - <90%
- 6 = 90% - 100%

PASI score calculation

Each of the body area scores is multiplied by the intensity score for the relevant body region (B1-B4) to gives four area and intensity scores (C1-C4).

The PASI score is the sum of the four area and intensity scores:

$$\text{PASI score} = C1 + C2 + C3 + C4.$$

17 Appendix 3: Physician Global Assessment

The physician will give a score on the participant's psoriasis disease activity, according to the following grades:

Induration (I) (averaged over all lesions; use the National Psoriasis Foundation Reference card for measurement)

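### Part A adverse events that change after the primary cut are not updated in the final summaries, and the listing of changes leaves out participants who withdrew during Part A

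*SAP*

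**What the plan says.** The SAP has two reporting points after the interim: a primary analysis at the end of Part A and a final analysis at the end of Part B.

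- **Primary analysis.** SAP 5.3.4.2 and 10.2 summarise events with onset up to the end of Part A.
- **Final analysis, summaries.** SAP 10.2: "In the final analysis at the end of Part B, only adverse events which started during Part B will be included in the summaries". SAP 5.3.4.2: "For the final analysis, only treatment related events which start in Part B will be included in the adverse event summaries". Later in 10.2: "In the final analysis only related TEAEs will be summarized by SOC and PT in the same manner as described above". The two sections differ on whether unrelated events are in scope, but both exclude events with Part A onset.
- **Final analysis, listings.** SAP 5.3.4.2 on the relevant data listings: "Only treatment related events which start in Part B and any Part A AEs which change in Part B will be included". Neither 5.3.4.2 nor 10.2 names a population for them.
- **Output list.** SAP 15.5.1 has two Part B adverse event tables, 14.4.3.1 and 14.4.3.2, both limited by title to related events starting in Part B. SAP 15.5.3 has one adverse event listing, 16.2.8.3, titled "Adverse Events Started or Changed in Part B", on the Part B population. SAP 7.1.6: "The Part B population will consist of all participants who entered Part B of the study".
- **Follow-up.** Protocol 6.2.1.4 requires each event to be followed until it resolves, is stable, or is judged chronic or not clinically significant, or until the participant dies or is lost. Withdrawal from the study is not among the stopping points.

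**The concern.** Safety is part of the primary objective (Protocol 2.1, SAP 4.1). The serious, fatal, grade 3 or higher and related counts are its main tables. The SAP expects Part A events to change after the cut, because it provides for listing them, yet it gives those changes no route into a summary table.

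Two consequences follow. First, a Part A event that later becomes serious or fatal, is regraded, or is re-attributed keeps its primary-cut status in Tables 14.3.1.x. Those tables can therefore disagree with the locked database. Second, a reader who turns to the listing for the changes finds only participants who entered Part B. A late change in someone who withdrew during Part A appears in no output designated for Part B.

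**Working it through.** The plan gives no figure to reproduce, so the check is mainly a trace of the rules.

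**1. Where can a changed Part A event appear at the final analysis?**

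| Output | Rule | Changed Part A event, participant entered Part B | Changed Part A event, participant withdrew in Part A |
|---|---|---|---|
| Tables 14.3.1.x (Safety population) | Part A onset, primary analysis (SAP 5.3.4.2, 10.2) | Status as at primary cut | Status as at primary cut |
| Tables 14.4.3.1 and 14.4.3.2 (Part B population) | Related, onset in Part B (SAP 15.5.1) | Not included | Not included |
| Listing 16.2.8.3 (Part B population) | Started or changed in Part B (SAP 15.5.3) | Listed | Not included |
| Listings 16.2.7.1.1 and 16.2.7.1.2 (Enrolled) | SAP 15.4; no statement in 5.3.4.2 or 10.2 that they are repeated | Updated only if re-run | Updated only if re-run |

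The first gap comes from 5.3.4.2 and 10.2. The second comes from the population column in 15.5.3 together with 7.1.6.

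**2. Do the row tags in SAP 10.2 close the first gap?** The eight related rows of the overview are tagged for both parts. The title of Table 14.4.3.1 still restricts them to events starting in Part B. Even if those rows were cumulative, the all-causality serious, fatal and grade rows are tagged for Part A alone.

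**3. Can events still change after the cut?** SAP 5.2 puts the primary analysis after all participants have completed Week 20. Dosing ends at Week 16 and routine adverse event reporting runs 28 days beyond that (Protocol 6.2.1.2), which is also about Week 20. For the last participants, an event starting late in that window has almost no follow-up at the cut. For participants who enrolled or withdrew early, much of the follow-up will already be in the database.

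**4. How many outputs depend on the fields that can change?**

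- Part A adverse event tables: 14.3.1.1.1 to 14.3.1.1.4 (4) + 14.3.1.2 to 14.3.1.8 (7) = 11.
- Tables defined by seriousness, grade, causality or fatal outcome: 14.3.1.1.1 and 14.3.1.2 to 14.3.1.6 = 6 of 11.
- Overview rows: 8 all-causality + 8 related = 16. Status-dependent: grade 2+, 3+, 4+, fatal and serious (5) + 8 related = 13 of 16.

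These counts show where a change would appear. They say nothing about how likely one is.

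**5. How far does one participant move a row?** Planned group sizes are from Protocol 7.3 and SAP 6.

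- One active dose: 1/50 = 2.0 points.
- Pooled placebo: 1/75 = 1.3 points.
- All EDP1815: 1/150 = 0.7 points.

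A participant already counted in the row moves nothing. The documents give no rate of change. If the net change in one active group were between -1 and +1 participant (an assumption), the row would be off by -2.0 to +2.0 points.

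**The case against.** The strongest reply is the opening sentence of SAP 15, which assigns every output in the sections that follow to the final analysis. Those sections include Tables 14.3.1.x and the Enrolled-set adverse event listings. Taken literally, this delivers the update. It has force: a reader might infer from 10.2 alone that the Part A tables certainly stay as they were, and the documents do not establish that. But the next sentence of SAP 15 contrasts final with interim, as SAP 12 does, so the likelier meaning is simply not interim. The literal reading also contradicts the word *only* in 10.2. What stands is a conflict that the SAP should resolve.

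SAP 10 and Protocol 7.6.5 assign safety summaries to the safety set. That settles a population, not which onset dates are summarised, and Tables 14.4.3.x depart from it anyway.

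Holding the Part A tables at the end of routine collection is also defensible. It keeps them at their status when the sponsor is unblinded. Site staff stay blinded through Part B (SAP 5.2), which limits the risk of bias in later causality judgements, but changes made after that point should be identifiable.

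Four stronger readings are tempting and are not supported:

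- *Counts are inflated because missing causality is treated as related (SAP 7.3.2).* This is a fallback. Causality is a collected field (Protocol 6.2.1.3), all eCRF items are to be completed (8.1), and lock follows query resolution (Protocol 8).
- *It is unclear whether participants with treatment failure or rebound entered Part B.* Protocol 3.1 has participants enter Part B after the Week 20 visit, and SAP 9.5.6 says that starting a new psoriasis treatment should lead to withdrawal. Together these largely settle it.
- *Related serious events learned of after discharge show that the tables go stale.* Such reports under Protocol 6.2.1.2 may be new events and not changes to Part A events.
- *The later visits to Week 28 or Week 40 measure the period at risk.* Protocol Table 6-2 schedules no adverse event review, so those visits do not define an adverse event follow-up window.

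**Conclusion.** The concern holds as a minor one. Under the stated rules of SAP 5.3.4.2 and 10.2, a Part A event whose seriousness, grade, causality or fatal outcome changes after the primary cut is not updated in any final summary. The listing meant to show such changes leaves out participants who withdrew during Part A. SAP 15 says something different if read literally, and the SAP does not reconcile the two.

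The effect is small: 2.0 points per participant in an active-dose row, on planned group sizes. The number of affected participants is unknown and probably low. For Part B entrants the change is at least listed. No efficacy result or halting decision depends on it. The conclusion rests on reading 10.2 as governing over the general sentence in SAP 15. If the literal SAP 15 reading were intended, the remaining defects would be the contradiction itself and the population of Listing 16.2.8.3.

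**What to change.** 1. Produce Listing 16.2.8.3 on the Safety population.
2. Amend SAP 5.3.4.2 and 10.2 so that Tables 14.3.1.1.1 to 14.3.1.8 are re-run on the Safety population at final lock, using event status at that lock. Footnote events whose status changed since the primary analysis. Tables 14.4.3.1 and 14.4.3.2 can stay as the Part B outputs.
3. Reword the opening of SAP 15 to state which outputs belong to the primary analysis and which to the final analysis.

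The cost is SAP wording and a re-run of existing programs. The downside is that some Part A counts may differ from the primary report. Changes made after the sponsor is unblinded also need to be flagged; the footnote serves both purposes.

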10.3 Deaths, Serious Adverse Events and other Significant Adverse Events

Treatment emergent SAEs, TEAEs leading to discontinuation of study drug or withdrawal from the study will be summarized separately by treatment, SOC and preferred term.

Serious AEs, fatal AEs and AEs leading to discontinuation of study drug will each be listed separately by participant.

No specific adverse events are considered to be of special interest for EDP1815.

10.4 Pregnancies

Pregnancy test data will be listed only.

10.5 Clinical Laboratory Evaluations

Central laboratory data will be used for all safety laboratory evaluations. [Table 10 \(Section 23\)](#) shows the parameters which will be collected and the units in which they will be supplied. Lab data will be transformed as appropriate to the International System of Units (SI units) as part of the SDTM programming and SI units will be used for all summaries.

Haematology and chemistry parameters will be summarised by visit, including change from baseline for all post-baseline visits.

The number and percentage of participants showing shifts from baseline to worst-case post-baseline with respect to the normal ranges will also be summarised for each haematology and chemistry parameter. Categories will be:

- Low
- Normal
- High

Haematology and chemistry values will also be flagged for potentially clinically important (PCI) values if they meet any of the criteria for Grade 2 or higher events according to CTCAE V5.0. The PCI criteria are listed in [Table 10 \(Section 23\)](#). The number and percentage of participants showing shifts from baseline to worst-case baseline with respect to PCI criteria will be summarised for all parameters where PCI criteria have been defined. Categories will be:

- Low
- Within range
- High

For both the normal range and PCI summaries, the determination of worst-case post-baseline will consider both scheduled and unscheduled assessments which occur after the first dose of study

treatment. Percentages will use the number of participants with at least one post-baseline assessment available as the denominator. If the baseline value is missing it will be assumed to be normal/within range. Worst-case can be either High or Low and if a participant has post-baseline values both above and below the normal range/PCI criteria then they will be counted in both relevant categories.

Haematology and chemistry data will be listed, including changes from baseline, normal ranges, flags for measurements outside the normal range, and flags for meeting PCI criteria. In addition, for participants who meet at least one PCI criteria, all values within the laboratory type (haematology or chemistry) will be listed separately.

Urinalysis data will be listed only.

